**4.4.2 Nivolumab +/- Ipilimumab Dosing Delays/Dose Modifications**

Toxicity grades per NCI-CTCAE Criteria v 4.03

Adverse Reaction	Severity	Dose Modification
Adrenal Insufficiency f	Grade 2 adrenal insufficiency	Withhold dose a
	Grade 3-4 adrenal insufficiency	Permanently discontinue c
Myocarditis	Grade 3-4 myocarditis	Permanently discontinue
Infusion Related Reaction	Grade 1-2 infusion related reaction	See section 4.5.2 for guidance
	Grade 3-4 infusion related reaction or anaphylaxis	Permanently discontinue
Uveitis, eye pain, blurred vision	Grade 2 that does not respond to topical therapy and does not improve to grade 1 severity within re-treatment period OR requires systemic treatment	Permanently discontinue
	Grade 3-4 uveitis or eye pain or blurred vision	Permanently discontinue
Colitis f	Grade 2 diarrhea or colitis	Withhold dose a
	Grade 3 diarrhea or colitis	Withhold dose a
	Grade 4 diarrhea or colitis	Permanently discontinue
Pneumonitis f	Grade 2 pneumonitis	Withhold dose a
	Grade 3 or 4 pneumonitis	Permanently discontinue
Hypophysitis f	Grade 2 hypophysitis	Withhold dose a
	Grade 3-4 hypophysitis	Permanently discontinue e
Type 1 Diabetes Mellitus f	Grade 3 hyperglycemia	Withhold dose a
	Grade 4 hyperglycemia	Permanently discontinue e
Nephritis and Renal Dysfunction f	Serum creatinine more than 1.5 and up to 6X ULN	Withhold dose a
	Serum creatinine more than 6X ULN	Permanently discontinue
Rash f	Grade 3 rash	Withhold dose a
	Grade 4 rash	Permanently discontinue
Encephalitis f	New-onset moderate or severe neurologic signs or symptoms	Withhold dose a
	Immune-mediated encephalitis	Permanently discontinue
Hepatitis	See section 4.4.2.1 for guidance	
Other f	Other Grade 3 adverse reaction b First occurrence	Withhold dose a
	Recurrence of same Grade 3 adverse reaction	Permanently discontinue
	Life-threatening or Grade 4 adverse reaction d	Permanently discontinue
	Requirement for 10 mg per day or greater prednisone or equivalent for more than 12 weeks	Permanently discontinue
	Persistent Grade 2 or 3 adverse reactions lasting 12 weeks or longer e	Permanently discontinue

a) Resume treatment when adverse reaction returns to Grade 0 or 1. If toxicity persists > 6 weeks, permanently discontinue nivolumab +/- ipilimumab. May discuss with Medical Monitor.

b) Except for grade 3 lymphopenia, leukopenia, isolated laboratory abnormalities without clinical significance, or amylase or lipase abnormality that is not associated with symptoms or clinical

manifestations of pancreatitis.

- c) Except for grade 2 fatigue, some subjects with baseline grade 1 LFT abnormalities who have grade 2 elevation of AST/ALT/bilirubin as described in 4.4.2.3, or subjects with grade 2-3 endocrine toxicities not described elsewhere in the table that are adequately treated with physiologic hormone replacement (e.g. hypothyroidism)
- d) Except for grade 4 lymphopenia, leukopenia, isolated electrolyte abnormalities without clinical significance that are corrected with supplementation/appropriate management within 72 hours of onset, or amylase or lipase abnormality that is not associated with symptoms or clinical manifestations of pancreatitis and decreases to <grade 4 within 1 week of onset.
- e) Selected subjects with transient episodes of grade 3-4 endocrine toxicities who are adequately treated and stabilized on physiologic hormone replacement or other supportive medications with improvement to grade 1-2 may not require discontinuation after discussion with and approval from the Medical Monitor.
- f) For additional management, including monitoring and use of corticosteroids or additional immunosuppressant therapies, recommend using guidelines for management of immunotherapy related toxicities, primarily the NCCN Management of Immunotherapy-Related Toxicities Version 1.2020. Section 11.2 has algorithms for possible management of selected toxicities, but management does not have to follow direction of Section 11.2.

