### **3.0 SUBJECT ELIGIBILITY**

#### **3.1 Inclusion Criteria**

Subjects must meet all of the inclusion criteria as listed below to participate in this study.

- 3.1.1 Histologically or cytologically confirmed colorectal adenocarcinoma, with unresectable metastatic or locally advanced disease documented on diagnostic imaging studies.
- 3.1.2 Previously received 1-2 prior lines of therapy. Subjects who relapse within 6 months of adjuvant chemotherapy comprised of oxaliplatin and a fluoropyrimidine will have their adjuvant therapy count as one prior line of therapy.
- 3.1.3 Confirmed wild-type in KRAS and NRAS codons 12, 13, 59, 61, 117, and 146; and BRAF codon 600, by standard of care testing of tumor specimen. Tissue used for testing may have been collected from primary or metastatic site.
- 3.1.4 Microsatellite stable as detected by PCR-based assay OR CLIA-certified sequencing methodology such as Foundation One; OR mismatch repair proficient as detected by immunohistochemistry showing intact nuclear staining of MLH1, MSH2, MSH6, and PMS2.
- 3.1.5 Radiographically measurable disease present per RECIST 1.1

- 3.1.6** Age  $\geq$  18 years at the time of consent.
- 3.1.7** Eastern Cooperative Oncology Group (ECOG) performance status 0 or 1.
- 3.1.8** Blood counts performed within 3 weeks prior to starting study therapy must have absolute neutrophil count  $\geq$  1,500/mm^3, platelets  $\geq$  100,000/mm^3, and hemoglobin  $\geq$  9 g/dL.

**\*Note:** Hematology and other lab parameters that are  $\leq$  grade 2 BUT still meet criteria for study entry are allowed. Furthermore, changes in laboratory parameters during the study should not be considered adverse events unless they meet criteria for dose modification(s) of study medication outlined by the protocol and/or worsen from baseline during therapy.

- 3.1.9** Liver function tests performed within 3 weeks prior to starting study therapy must have total bilirubin  $\leq$  1.5 x upper limit of normal (ULN), alanine aminotransferase and aspartate aminotransferase  $\leq$  3 x ULN, and albumin  $\geq$  2.5 g/dL.
- 3.1.10** Serum creatinine performed within 3 weeks prior to starting study therapy must be  $\leq$  1.5 x ULN, or have calculated creatinine clearance (using Cockcroft-Gault formula provided in Appendix 11.3) of  $\geq$  50 mL/minute.

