**4.4.2.1 Nivolumab and/or Ipilimumab Dose Modifications/Delays for Liver Toxicity**

Recognizing that mCRC is often associated with the presence of liver metastases at baseline, the following criteria will be used for dose modifications/delays of nivolumab and/or ipilimumab for liver toxicity.

Baseline Liver Function Test (NCI-CTCAEv4.03 grade)	Adverse Reaction Severity	Dose Modification *
AST or ALT normal	AST or ALT $\geq 3$ X ULN to $\leq 5$ X ULN	Withhold dose a
	AST or ALT $> 5$ X ULN	Permanently discontinue
AST or ALT 1.1 to $\leq 2.5$ X ULN (Grade 1)	AST or ALT $\geq 5$ X ULN to $\leq 8$ X ULN	Withhold dose a
	AST or ALT $> 8$ X ULN	Permanently discontinue
Total Bilirubin normal	$> 1.5$ to $\leq 3$ X ULN	Withhold dose a
	$> 3$ X ULN	Permanently discontinue
Total Bilirubin 1.1 to $\leq 1.5$ X ULN (Grade 1)	$\geq 3$ to $5$ X ULN	Withhold dose a
	$> 5$ X ULN	Permanently discontinue

a) Resume treatment when adverse reaction returns to Grade 0 or 1. If toxicity persists  $> 6$  weeks, permanently discontinue nivolumab +/- ipilimumab

\* For additional management, including monitoring and use of corticosteroids or additional immunosuppressant therapies, recommend using guidelines for management of immunotherapy related toxicities, primarily the NCCN Management of Immunotherapy-Related Toxicities Version 1.2020. Section 11.2 has algorithms for possible management of selected toxicities, but management does not have to follow direction of Section 11.2.

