#### **4.4.2.3 Criteria to Resume Nivolumab +/- Ipilimumab Treatment**

Subjects may resume treatment with study drug when the drug-related AE(s) resolve to Grade  $\leq 1$  or baseline value, with the following exceptions:

- Subjects may resume treatment in the presence of Grade 2 fatigue
- Subjects who have not experienced a Grade 3 drug-related skin AE may resume treatment in the presence of Grade 2 skin toxicity
- Subjects with baseline Grade 1 AST/ALT or total bilirubin who require dose delays for reasons other than a 2-grade shift in AST/ALT or total bilirubin may resume treatment in the presence of Grade 2 AST/ALT OR total bilirubin
- Drug-related pulmonary toxicity, diarrhea, or colitis, must have resolved to baseline before treatment is resumed. Subjects with persistent Grade 1 pneumonitis after completion of a steroid taper over at least 1 month may be eligible for retreatment if investigator allows.
- Subjects with drug-related endocrinopathies adequately controlled with only physiologic hormone replacement may resume treatment if the investigator allows it, but this should be documented clearly in the electronic case report form (eCRF).

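### Footnote a of 4.4.2 allows restart of nivolumab +/- ipilimumab at Grade 1 diarrhea, colitis or pneumonitis, where 4.4.2.3 asks for return to baseline

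*Combined protocol and SAP*

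**What the plan says.** In the 4.4.2 table, the row for "Grade 2 diarrhea or colitis", the matching Grade 3 row and the Grade 2 pneumonitis row all say to withhold the dose, with footnote a. The footnote reads "Resume treatment when adverse reaction returns to Grade 0 or 1. If toxicity persists > 6 weeks, permanently discontinue nivolumab +/- ipilimumab", followed by "May discuss with Medical Monitor". The liver table in 4.4.2.1 has its own footnote a with the same restart rule ("Resume treatment when adverse reaction returns to Grade 0 or 1. If toxicity persists" and so on), but without the Medical Monitor sentence.

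Section 4.4.2.3 sets the restart criteria separately. Its general level is Grade 1 or lower "or baseline value, with the following exceptions". One of those exceptions is "Drug-related pulmonary toxicity, diarrhea, or colitis, must have resolved to baseline before treatment is resumed". The same bullet lets persistent Grade 1 pneumonitis be retreated after a completed steroid taper of at least 1 month, if the investigator allows.

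Section 4.4.2.2 says that doses are delayed under 4.4.2 and 4.4.2.1 and resumed when re-treatment criteria are met; it gives no section number for the latter. Section 4.4.2.4 sends sites to 4.4.2 and 4.4.2.1 for mandatory dosing guidance.

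**The concern.** Two restart levels apply to the same held event, and the looser one is attached to the row that a site reads when it holds the dose. A site that follows the footnote may restart both checkpoint inhibitors while drug-related colitis is still present at Grade 1. A site that follows 4.4.2.3 keeps holding. If the hold passes 6 weeks, 4.4.2.3.1 requires that site to stop study therapy, unless an exception in 4.4.2.5 applies. In a multicenter trial, similar subjects could be managed differently, with both sites able to cite the protocol. What is at stake is subject safety and consistent conduct, not the analysis of the primary endpoint.

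**Working it through.** No arithmetic applies. The check sets the two rules side by side and then looks for text that settles the difference.

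**Step 1: which holds are affected.** Footnote a covers the Grade 2 and Grade 3 diarrhea/colitis rows and the Grade 2 pneumonitis row. Pneumonitis of Grade 3 or 4 and colitis of Grade 4 are permanent stops in the table. Section 4.4.2.5 also stops a Grade 3 non-skin drug-related event that lasts more than 7 days. Grade 2 events are therefore the main case.

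**Step 2: what each rule answers.**

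| Held event and baseline | State now | Footnote a | 4.4.2.3 | Same answer? |
|---|---|---|---|---|
| Colitis, no diarrhea at baseline | Grade 0 | Restart | Restart | Yes |
| Colitis, no diarrhea at baseline | Grade 1 | Restart | Hold | **No** |
| Diarrhea, Grade 1 at baseline (3.2.6 allows residual Grade 1 toxicity) | Grade 1 | Restart | Restart | Yes |
| Pneumonitis (active non-infectious pneumonitis is excluded by 3.2.4, so baseline is in effect none) | Grade 1, taper of at least 1 month not completed or investigator has not agreed | Restart | Hold | **No** |
| Pneumonitis | Grade 1, taper completed and investigator agrees | Restart | Restart possible | Yes |

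The second row needs no assumption about grade limits or laboratory ranges.

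**Step 3: is precedence stated?** Section 4.4.2.2 points to re-treatment criteria, and 4.4.2.3 is the section whose title fits. Footnote c of the table cites 4.4.2.3; footnote a does not. Section 4.4.2.4 applies the word mandatory to the two sections that hold the tables. No sentence says which restart level prevails.

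**Step 4: do other provisions set the level?** The Medical Monitor sentence is optional. Section 4.4.2.5 allows longer delays for steroid tapers, asks the investigator to weigh resumption with care, and says that in select cases such as colitis ipilimumab may be dropped while nivolumab continues. Section 4.5.3 asks for a taper of at least 1 month once corticosteroids are used. None of these gives the grade at which a held dose may resume.

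**The case against.** The strongest reply is that the documents, read as a whole, already give the right answer. Section 4.4.2.2 separates the roles: the tables say when to hold, and the re-treatment criteria say when to resume. Section 4.4.2.3 opens with nearly the same general level as the footnote and then lists exceptions, so the specific rule should prevail over the general one. It is itself a subsection of 4.4.2, so the mandatory label in 4.4.2.4 can be read to include it. A site that waits for baseline in a subject with no baseline diarrhea also satisfies the footnote. And in a steroid-treated case the 4.5.3 taper makes an early restart unlikely.

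Much of this stands. It is why 4.4.2.3 is the better reading and why the point is minor. It does not remove the conflict: footnote a is worded as a complete instruction on named rows, and a site could equally take the row-level footnote as the specific rule. The taper affects timing, but leaves open what to do if Grade 1 colitis remains when it ends.

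A reader might also infer a conflict in the other direction, because 4.4.2.3 accepts a return to the baseline value and the footnote does not. On that view a subject admitted with AST/ALT between 2.5 and 3 x ULN could be kept on hold at his own entry value. The documents do not support this as a main claim. The 4.4.2.1 table has no row for entry above 2.5 x ULN, so its footnote attaches to no hold for that subject. The note under 3.1.8 also says that laboratory changes are not adverse events unless they meet dose-modification criteria and/or worsen from baseline. A creatinine version would need a Grade 1 limit that the documents do not state.

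**Conclusion.** Wrong as written, minor, and a matter of patient safety. For held diarrhea or colitis, and for Grade 2 pneumonitis without the taper and investigator agreement, footnote a of 4.4.2 permits a restart that 4.4.2.3 does not. The finding rests on the wording alone and assumes only that a site may act on the footnote as printed.

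No frequency can be attached. Section 5.3.8 lists diarrhea and colitis among events in at least 5% of subjects on ipilimumab, but that is any grade. The share held and then left at Grade 1 above baseline at a dosing visit is not given. Two stronger conclusions do not follow:

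- A reader might infer a large loss of doses before the 12-week scan. That compares a rapid restart with a hold that ends in a permanent stop, and passes over the taper in 4.5.3 and the taper exception in 4.4.2.5.
- A reader might infer that the toxicity count in 8.3 is compromised. A subject's count could differ only if the residual event kept the hold going beyond 6 weeks with no 4.4.2.5 exception, and the documents give no basis for estimating that number.

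Sample size, alpha, power and the 8.3 boundaries do not change.

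**What to change.** In footnote a of 4.4.2, replace the first sentence with: *Resume treatment when the criteria in 4.4.2.3 are met (including resolution to baseline for drug-related pulmonary toxicity, diarrhea and colitis, with the Grade 1 pneumonitis exception given there).* Keep the 6-week stop and add *except as allowed in 4.4.2.5*, which matches 4.4.2.3.1. Keep the Medical Monitor sentence.

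Use the same two cross-references in footnote a of 4.4.2.1 for consistency, without adding a Medical Monitor clause, since the plan has none there. The other exceptions in 4.4.2.3, such as Grade 2 fatigue, would then apply through the footnote as 4.4.2.3 already provides.

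The cost is an edit to two footnotes in one protocol amendment. No tests, visits, eligibility criteria or statistical sections change.

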**4.4.2.1 Nivolumab and/or Ipilimumab Dose Modifications/Delays for Liver Toxicity**

Recognizing that mCRC is often associated with the presence of liver metastases at baseline, the following criteria will be used for dose modifications/delays of nivolumab and/or ipilimumab for liver toxicity.

Baseline Liver Function Test (NCI-CTCAEv4.03 grade)	Adverse Reaction Severity	Dose Modification *
AST or ALT normal	AST or ALT $\geq 3$ X ULN to $\leq 5$ X ULN	Withhold dose a
	AST or ALT $> 5$ X ULN	Permanently discontinue
AST or ALT 1.1 to $\leq 2.5$ X ULN (Grade 1)	AST or ALT $\geq 5$ X ULN to $\leq 8$ X ULN	Withhold dose a
	AST or ALT $> 8$ X ULN	Permanently discontinue
Total Bilirubin normal	$> 1.5$ to $\leq 3$ X ULN	Withhold dose a
	$> 3$ X ULN	Permanently discontinue
Total Bilirubin 1.1 to $\leq 1.5$ X ULN (Grade 1)	$\geq 3$ to $5$ X ULN	Withhold dose a
	$> 5$ X ULN	Permanently discontinue

a) Resume treatment when adverse reaction returns to Grade 0 or 1. If toxicity persists  $> 6$  weeks, permanently discontinue nivolumab +/- ipilimumab

\* For additional management, including monitoring and use of corticosteroids or additional immunosuppressant therapies, recommend using guidelines for management of immunotherapy related toxicities, primarily the NCCN Management of Immunotherapy-Related Toxicities Version 1.2020. Section 11.2 has algorithms for possible management of selected toxicities, but management does not have to follow direction of Section 11.2.

**4.4.2.2 Dose Delay Criteria for Nivolumab +/- Ipilimumab**

Because of the potential for clinically meaningful nivolumab-related AEs requiring early recognition and prompt intervention, management algorithms have been developed for suspected AEs of selected categories [see current Investigator Brochure and Appendix 11.2]. Hepatotoxicity guidelines are provided in the section above.

Dose delay criteria apply for all drug-related adverse events related to nivolumab and/or ipilimumab (regardless of whether or not the event is attributed to nivolumab, ipilimumab, or both). If both nivolumab and ipilimumab are being administered, both must be delayed until treatment can resume.

**Nivolumab +/- ipilimumab administration should be delayed per the criteria in 4.4.2 and 4.4.2.1.**

Additionally, nivolumab +/- ipilimumab should be held in the event of any AE, laboratory abnormality, or intercurrent illness which, in the judgment of the investigator, warrants delaying the dose of study medication.

**Subjects who require delay of nivolumab +/- ipilimumab should be re-evaluated weekly or more frequently if clinically indicated and resume nivolumab +/- ipilimumab dosing when re-treatment criteria are met.**

#### **4.4.2.3 Criteria to Resume Nivolumab +/- Ipilimumab Treatment**

Subjects may resume treatment with study drug when the drug-related AE(s) resolve to Grade  $\leq 1$  or baseline value, with the following exceptions:

- Subjects may resume treatment in the presence of Grade 2 fatigue
- Subjects who have not experienced a Grade 3 drug-related skin AE may resume treatment in the presence of Grade 2 skin toxicity
- Subjects with baseline Grade 1 AST/ALT or total bilirubin who require dose delays for reasons other than a 2-grade shift in AST/ALT or total bilirubin may resume treatment in the presence of Grade 2 AST/ALT OR total bilirubin
- Drug-related pulmonary toxicity, diarrhea, or colitis, must have resolved to baseline before treatment is resumed. Subjects with persistent Grade 1 pneumonitis after completion of a steroid taper over at least 1 month may be eligible for retreatment if investigator allows.
- Subjects with drug-related endocrinopathies adequately controlled with only physiologic hormone replacement may resume treatment if the investigator allows it, but this should be documented clearly in the electronic case report form (eCRF).

##### **4.4.2.3.1 Guidance on Cycle Counting after Treatment Delay**

If the criteria to resume treatment are met, and treatment was delayed for up to one week ( $\leq 7$  days), make up the missed treatment visit. If treatment was delayed for 8-42 days, skip the missed treatment(s) and resume treatment at the next relevant cycle/day treatment visit, unless the subject is  $\geq 42$  days from the last dose of ipilimumab, in which case resume treatment at day 1 of the next treatment cycle.

If treatment is delayed or interrupted for  $> 6$  weeks due to toxicity, adverse effect, or medical comorbidity, the subject must be permanently discontinued from study therapy, except as specified in the discontinuation section 4.4.2.5.

#### **4.4.2.4 Management Algorithms for Immune-related Events for Nivolumab +/- Ipilimumab**

Guidelines for the management of immune-related events can be found in the current Nivolumab Investigator Brochure AND in the approved USPI in the US.

Immuno-oncology (I-O) agents are associated with AEs that can differ in severity and duration than AEs caused by other therapeutic classes. Nivolumab is considered an I-O agent in this protocol. Early recognition and management of AEs associated with immuno-oncology agents may mitigate severe toxicity. Management algorithms have been developed to assist investigators in assessing and managing the following groups of AEs:

For mandatory guidance on dosing of nivolumab and/or ipilimumab with specified immune related adverse events, please refer to section 4.4.2 and

section 4.4.2.1. For additional management, including monitoring and use of corticosteroids or additional immunosuppressant therapies, recommend using guidelines for management of immunotherapy related toxicities, primarily the NCCN Management of Immunotherapy-Related Toxicities Version 1.2020. Section 11.2 has algorithms for possible further management of selected toxicities, but management does not have to follow direction of Section 11.2. Instead, these algorithms are only an additional resource to complement other guidelines and the Investigator's medical judgment.

  - Grade 4 drug-related endocrinopathy adverse events, such as adrenal insufficiency, ACTH deficiency, hyper- or hypothyroidism, or glucose intolerance, which resolve or are adequately controlled with physiologic hormone replacement (corticosteroids, thyroid hormones) or glucose-controlling agents, respectively, may not require discontinuation after discussion with and approval from the Investigator
- Any dosing interruption lasting > 6 weeks with the following exceptions:
  - Dosing delays or interruptions to allow for prolonged steroid tapers to manage drug-related adverse events are allowed. Prior to re-initiating treatment in a subject with a dosing interruption lasting > 6 weeks, the Investigator must be consulted. Tumor assessments should continue as per protocol even if dosing is interrupted or delayed
  - Dosing interruptions or delays lasting > 6 weeks that occur for non-drug-related reasons may be allowed if approved by the Investigator. Prior to re-initiating treatment in a subject with a dosing interruption lasting > 6 weeks, the Investigator must be consulted. Tumor assessments should continue as per protocol even if dosing is interrupted
- Any adverse event, laboratory abnormality, or intercurrent illness which, in the judgment of the Investigator, presents a substantial clinical risk to the subject with continued nivolumab and ipilimumab dosing

Additionally, after any immune related adverse event that does not meet the mandatory discontinuation requirement, the treating investigator should carefully consider the safety of resuming nivolumab and/or ipilimumab. In select cases, like for colitis, it would be appropriate to discontinue ipilimumab but continue nivolumab. This should be discussed with the medical monitor, and decisions should use guidelines for rechallenge after immune-related adverse events, such as found in the NCCN Management of Immunotherapy-Related Toxicities Version 1.2020.

